#### **5.4 Co-enrollment Guidelines**

As indicated in Sections [5.2](#) and [5.3](#), participants must not take part in other research studies involving drugs, medical devices, genital or rectal products, or vaccines after the Screening Visit and while taking part in MTN-035 unless approved by the Protocol Safety Review Team (PSRT). Participation in the following types of studies may be allowed at the discretion of the IoR/designee:

- Participants may take part in ancillary studies if approved by MTN-035 PSRT
- Participants who become infected with HIV may take part in observational and/or interventional studies for HIV-positive persons

Should any participant report concurrent participation in contraindicated studies after enrolling in MTN-035, the IoR/designee will consult the PSRT regarding ongoing product use and other potential safety considerations associated with co-enrollment.

## 6 STUDY PRODUCT

### 6.1 Regimen

Participants will be randomized to one of six study product administration sequences (Sequence A-F). Each sequence will consist of three four-week periods of study product administration, with one week between each four-week period. The duration of product administration including the two washout periods is approximately 14 weeks.

**Table 3: Study Product Regimen**

Sequence	N	Period 1 (4 weeks)	Washout period (~1 week)	Period 2 (4 weeks)	Washout period (~1 week)	Period 3 (4 weeks)
A	35	Rectal insert	--	Rectal douche	--	Rectal suppository
B	35	Rectal douche	--	Rectal suppository	--	Rectal insert
C	35	Rectal suppository	--	Rectal insert	--	Rectal douche
D	35	Rectal insert	--	Rectal suppository	--	Rectal douche
E	35	Rectal douche	--	Rectal insert	--	Rectal suppository
F	35	Rectal suppository	--	Rectal douche	--	Rectal insert

### 6.2 Administration

Each participant will receive study product that includes placebo inserts, placebo suppositories, and placebo (water) douches for pericoital rectal administration. The products will be administered in order of the assigned sequence. It is recommended that participants insert one dose of the study product between 30 minutes and 3 hours prior to RAI, and that they not insert more than one dose in 24 hours. The study product should be administered following the participant's usual pre-RAI practices. If a participant does not engage in RAI in a given week, they will be asked to insert a dose of the product in the absence of RAI. Participants will self-administer the first dose of each product in the clinic to ensure correct administration and tolerability.

### **6.2.1 Placebo inserts and suppositories**

Participants will be instructed to insert in the rectum a placebo insert or suppository prior to RAI. If a dose is missed, participants will be instructed to wait to take a dose at the next occurrence of RAI. Furthermore, if no RAI activity occurs at all in a given 7-day period, participants will be instructed to take a dose on the seventh day in the absence of RAI. Participants will be provided instructions on proper insertion of the insert and suppository.

### **6.2.2 Placebo rectal douche**

Participants will be instructed to insert in the rectum a placebo douche prior to RAI. If a dose is missed, participants will be instructed to wait to take a dose at the next occurrence of RAI, or if no other RAI activity occurs in that 7-day period, to take a dose in the absence of RAI. Furthermore, if no RAI activity occurs at all in a given 7-day period, participants will be instructed to take a dose on the seventh day in the absence of RAI. Participants will be provided instructions on preparation and proper insertion of the douche.

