#### PROTOCOL SUMMARY

Short Title:	Rectal Microbicide Acceptability, Tolerability, and Adherence
Funders:	Division of AIDS, NIAID, NIMH, NICHD, US NIH
Protocol Chair:	[name], MPH
Sample Size:	MTN-035 will enroll approximately 210 participants
Study Population:	HIV-uninfected cisgender men, transgender men (TGM) and transgender women (TGW) aged 18-35 years who engage in receptive anal intercourse (RAI)
Study sites:	Sites selected by MTN Executive Committee
Study Design:	Multi-site, randomized-sequence, three-period, open label crossover study
Study Duration:	Approximately 3.5 months of follow-up with a projected accrual period of 9-12 months
Study Products:	Placebo rectal insert Placebo rectal douche Placebo rectal suppository
Study Regimen:	Participants will be randomized (1:1:1:1:1:1) to study product sequences A-F (see Table 1 below). At the start of each 4-week product use period, they will receive either rectal inserts, rectal douches, or rectal suppositories and be instructed to use their assigned study product prior to each RAI encounter during that period. Participants who do not have RAI in a given week will be asked to use the product without sex. There will be a 1-week washout period between each of the three product use periods.

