## 5.2 Inclusion Criteria

Individuals who meet the following criteria are eligible for study inclusion:

1. Men (cis or transgender) and TGW who are 18-35 years old at Screening, verified per site SOP
2. Able and willing to provide written informed consent
3. HIV-1/2 uninfected at Screening and Enrollment, per applicable algorithm in [Appendix II](#) and willing to receive HIV test results
4. Able and willing to provide adequate locator information, as defined in site SOP
5. Available to return for all study visits and willing to comply with study participation requirements

6. In general good health at Screening and Enrollment, as determined by the site Investigator of Record (IoR) or designee
7. At Screening, history of consensual RAI at least three times in the past three months and expecting to maintain at least this frequency of RAI during study participation per participant report
8. Willing to not take part in other research studies involving drugs, medical devices, genital or rectal products, or vaccines for the duration of study participation (including the time between Screening and Enrollment)
9. For individuals who can get pregnant (i.e., TGM with a female reproductive system): a negative pregnancy test at Screening and Enrollment
10. For individuals who can get pregnant: Per participant report at Enrollment, using an effective method of contraception for at least 30 days (inclusive) prior to Enrollment and intending to use an effective method for the duration of study participation; effective methods include:
  - a) Hormonal methods
  - b) Intrauterine device (IUD) inserted at least 30 days prior to Enrollment (but not past the maximum length of recommended usage according to package instructions)
  - c) Sterilization (of participant or, if in a monogamous relationship, of partner, as defined in site SOPs)
  - d) Abstinence from RVI for 90 days prior to Enrollment, and intention to abstain from RVI for the duration of study participation

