# 7 STUDY PROCEDURES

An overview of the study visit and evaluations schedule is presented in [Appendix I](#). Presented in this section is additional information on visit-specific study procedures. Detailed instructions to guide and standardize procedures as well as information regarding the study visit windows are provided in the MTN-035 SSP Manual available at <http://www.mtnstopshiv.org/research/studies>.

Figure 2: MTN-035 Study Visit Schedule

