8. PRIMARY ENDPOINTS

The acceptability, tolerability and adherence primary endpoints will be evaluated on the per-protocol subset of participants, i.e. participants who received all three study products and completed the corresponding PUEV, and thus provide relevant data from all three periods of study. Assessment of these endpoints will be based on responses from the participants to the computer assisted self-interviews (CASI) at the three PUEVs (Visits 3, 5 and 7). To aid in the interpretation of the resulting analyses, baseline characteristics of the per-protocol subset of participants including, but not limited to, study site, sequence, sex/gender, and age will be described and compared to those of participants who were lost to follow-up.

Acceptability and Tolerability

The acceptability and tolerability endpoint will be based on question H1 of the CASI:

“Think about the positive and negative experiences you have had using the rectal Insert during the past 4 week period. If this rectal insert was available and it provided some protection against HIV, how likely would you be to use it before receptive anal sex?”.

Responses to this question for each product were captured from visual Likert scale from 1 (very unlikely) to 10 (very likely). Participants’ responses corresponding to the three product use periods will be displayed in tables by study product, by study product and site and by study product and randomization sequence.

To compare acceptability and tolerability between study products, the endpoint will be operationalized as binary, with scores 1 to 6 grouped as “low acceptability” and scores 7 – 10 as “high acceptability”. Number and percentage of participants giving a “high acceptability” score will be display in tables by study product, with exact binomial 95% confidence intervals (Clopper-Pearson method).

Adherence

Two endpoints related to adherence will be assessed: adherence to use per-protocol and adherence to use per-anal-sex-act. These are defined as follows:

1. **Adherence to use per-protocol:** Number and proportion of participants who reported not having missed a rectal [enema/douche, insert or suppository] application in the previous 4 weeks, according to the participants’ response to question B0 of the CASI:

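### Only douche users are told to make up a missed pre-RAI dose in the same week, which can tilt the exploratory comparison of weekly adherence towards the douche, depending on how question B0 is read

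*Protocol*

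**What the plan says.** The Protocol Summary describes one regimen for all three products: use before each RAI, and "Participants who do not have RAI in a given week will be asked to use the product without sex". Section 6.2 repeats this in general terms. The product-specific sections then differ.

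- **Insert and suppository (6.2.1):** "If a dose is missed, participants will be instructed to wait to take a dose at the next occurrence of RAI". A seventh-day dose without RAI is required only "if no RAI activity occurs at all in a given 7-day period".
- **Douche (6.2.2):** the same wait-for-next-RAI rule and the same seventh-day rule, plus a further option after a missed dose: "or if no other RAI activity occurs in that 7-day period, to take a dose in the absence of RAI".

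SAP Section 8 defines per-protocol adherence as "Number and proportion of participants who reported not having missed a rectal" application in the previous 4 weeks, taken from CASI question B0. B0 is worded identically for every product. It first reminds the participant of a weekly minimum of one insertion, then asks in how many of the four weeks an application was missed. Zero weeks counts as fully adherent. SAP Section 10 estimates odds ratios of full adherence between products from a logistic model with a participant random intercept. Protocol 10.7.1 plans no between-product comparison in the primary analysis.

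**The concern.** Take a week with one RAI, the pre-RAI dose missed, and no further RAI. The seventh-day rule does not apply, because RAI did occur. A douche user who follows the protocol then takes a dose; an insert or suppository user who follows the protocol does not. The same behaviour therefore leaves a week with an application for one product and a week without for the other two.

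If B0 is answered as weeks without any application, that week counts against the insert and suppository but not against the douche. The difference travels with the product, so neither the randomised sequence nor the participant random intercept can remove it. Part of a douche advantage in the Section 10 odds ratio could then reflect the instruction and not the product. Someone who reads only the SAP would not know that the instructions differed.

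**Working it through.** The plan gives no figure for this effect, so the size below is an illustration.

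**Inputs from the documents**
- Zero missed weeks on B0 means fully adherent (SAP 8).
- "Participants will self-administer the first dose of each product in the clinic to ensure correct administration and tolerability" (Protocol 6.2). I take this dose to cover week 1, leaving 3 weeks at risk.
- Minimum RAI frequency at entry: "history of consensual RAI at least three times in the past three months" (Protocol 5.2), that is 3/13 = 0.23 per week.

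**Assumptions (not in the documents)**
- RAI per week is Poisson with mean L.
- Every pre-RAI and seventh-day dose is missed with the same probability m, for everyone and every product.
- Douche users carry out the make-up dose with probability q; insert and suppository users never do.
- B0 is answered as weeks without any application.

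**Formulas**
- Week with RAI but no dose taken: w = exp(-L(1-m)) - exp(-L)
- Week without RAI, seventh-day dose missed: s = m·exp(-L)
- P(zero missed weeks), insert or suppository: (1 - w - s)^3
- P(zero missed weeks), douche: (1 - w(1-q) - s)^3

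**Worked case, L = 1, m = 0.10, q = 0.80**
- w = 0.4066 - 0.3679 = 0.0387; s = 0.0368
- Insert or suppository: 0.9245^3 = 79.0%
- Douche: (1 - 0.0077 - 0.0368)^3 = 0.9555^3 = 87.2%
- Gap 8.2 points; odds ratio (0.872/0.128)/(0.790/0.210) = 1.81

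**Range, q = 25% to 80%**

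| RAI/week | Missed | Insert or suppository | Douche | Gap (points) | Odds ratio |
|---|---|---|---|---|---|
| 0.23 | 5% | 86.0% | 86.7-88.0% | 0.6-2.0 | 1.05-1.20 |
| 0.23 | 10% | 73.4% | 74.5-77.1% | 1.1-3.7 | 1.06-1.22 |
| 1 | 5% | 89.2% | 90.6-93.5% | 1.3-4.3 | 1.16-1.73 |
| 1 | 10% | 79.0% | 81.5-87.2% | 2.5-8.2 | 1.17-1.81 |
| 2 | 10% | 87.5% | 89.6-94.3% | 2.1-6.7 | 1.23-2.34 |
| 3 | 10% | 93.4% | 94.7-97.5% | 1.3-4.1 | 1.25-2.72 |

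The larger odds ratios in the last two rows come from a high baseline, not from a larger gap.

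**Sensitivity, at 10% missed**
- *Miss rate varies between people* (assumed Beta(0.1, 0.9), mean still 10%): the gap falls to 0.4-1.4 points at 0.23 RAI/week and 1.2-4.8 at 1 RAI/week.
- *Insert and suppository users make up 40% against 80% for the douche*, at 1 RAI/week: their rate is (1 - 0.0387×0.6 - 0.0368)^3 = 83.1%, and the gap about halves, from 8.2 to 4.2 points.
- *Half of respondents report any missed dose*: every gap halves. At 1 RAI/week the odds ratio is 1.07-1.24.
- *All respondents report any missed dose*: the gap is zero.
- *Clinic dose not counted, so 4 weeks at risk*: the largest gap rises from 8.2 to 10.3 points.

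For scale, the protocol's exact 95% interval at 80% observed in 200 participants is 74-85%; recomputing gives 73.8-85.3%.

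**The case against.** The strongest reply is that the effect needs one particular reading of B0. Someone who skipped the pre-RAI dose and dosed later without RAI did miss an application, and both the question and the SAP endpoint definition can be taken that way. On that reading the tilt is exactly zero. This stands. The weekly-minimum reminder makes the other reading plausible but does not settle it.

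Second, that reminder addresses users of all products. If it reflects what participants were actually told, insert and suppository users also had a reason to dose in such a week. In sequences A, B, E and F the douche precedes at least one other product, so the habit could carry forward. The SSP Manual, which is said to contain "Detailed instructions to guide and standardize procedures", is not among the documents and may have harmonised the instructions. This also stands, and it is why the calculated gaps lean towards the high side.

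Third, the odds ratios above are marginal, while SAP Section 10 plans conditional ones from a random-intercept model. They show direction and rough scale and do not predict the planned estimate.

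Fourth, each product's own rate is a fair description of adherence under its own instruction, and the stated goal is to estimate rates. That is correct for the primary tables. It does not cover Section 10, which sets the products against each other on one yardstick.

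A reader might infer that the plan has a demonstrated bias in favour of the douche, or that acceptability and safety are affected too. The documents do not support either. The bias is conditional on how B0 is answered, and neither the acceptability rating nor the safety endpoint is defined by missed weeks.

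**Conclusion.** The difference between 6.2.1 and 6.2.2 is real, unexplained, and not closed by the seventh-day rule or the general text in 6.2. It can favour the douche on zero missed weeks and on the exploratory odds ratio, but only if B0 is answered as weeks without any application.

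The documents give no miss rate, make-up rate or weekly RAI distribution, so no size can be claimed as established. The 0.6 to 8 point range is conditional on the assumptions listed above. Realistic departures from a common miss rate and from make-up by douche users only reduce it. It would be wrong to cite the odds ratios of 2 or more as evidence of a large effect.

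The point is minor. One exploratory estimate is exposed. Per-sex-act adherence (B2 divided by B1) is untouched, because a dose taken without RAI does not enter it.

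**What to change.** Add the make-up clause of 6.2.2 to 6.2.1, so that all three products carry the same missed-dose instruction. This costs one clause of protocol wording and removes the product-tied difference whichever way B0 is read.

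The COVID-19 text in SAP 3.2 shows that dosing was already under way when the SAP was written, so the change may come too late. In that case, check the SSP Manual first. If it did not harmonise the instructions, put one sentence beside the per-protocol adherence odds ratio stating that they differed, and read that odds ratio together with the per-sex-act comparison already planned in SAP Section 10. This needs no new data or analysis.

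Do not substitute the per-sex-act comparison for the weekly one. It leaves out participant-periods with no RAI. Under the Poisson assumption their share is exp(-4L): about 40% of 4-week periods at 0.23 RAI/week and about 2% at 1 RAI/week.

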## **6.3 Study Product Formulation**

Study products should be stored at controlled room temperature 20° - 25°C (68° - 77°F) until dispensed for use. Excursions between 15° – 30°C (59° – 86°F) are allowed.

### **6.3.1 Placebo rectal insert**

The placebo rectal insert is formulated into white to off-white uncoated solid dosage forms in a bullet shape. The insert contains the following inactive excipients: isomalt, xylitol, sodium CMC, povidone, hydroxypropyl methylcellulose, poloxamer 188, sodium stearyl fumarate and magnesium stearate. The insert is 1.5 cm (0.6 inches) long, 0.7 cm (0.28 inches) wide, 0.6 cm (0.23 inches) in height, and approximately 500 mg in weight. The rectal insert is manufactured under current Good Manufacturing Practice (cGMP) under CONRAD oversight. The insert is stored in a white induction-sealed HDPE bottle along with polyester coil and a desiccant at controlled room temperature (see temperature details above).

### **6.3.2 Placebo rectal douche**

Participants will fill the enema bottle with approximately 120 mL of clean tap water or bottled water. The enema bottles used in this study are commercially available 125 mL enema bottles that meet US Pharmacopeia (USP) standards and contain no heavy metals, no phthalates, and are bisphenol A (BPA) free.

### **6.3.3 Placebo rectal suppository**

The rectal suppository is approximately 3-3.8 cm (1.2-1.5 inches) long and 2 grams in weight. The placebo rectal suppository consists of a Witepsol® H5 (IOI Oleochemical) base and contains 15% diglyceride and not more than 1% monoglyceride content. The rectal suppository will be manufactured under current Good Manufacturing Practice (cGMP). The suppository is stored at controlled room temperature (see temperature details above).

## **6.4 Study Product Supply and Accountability**

### **6.4.1 Study Product Supply**

#### ***Placebo Rectal Insert***

CONRAD will oversee the manufacture of the placebo inserts by CoreRx (Clearwater, FL)

#### ***Placebo Rectal Douche***

Participants will be provided commercially available 125 mL enema bottles with pre-lubricated tips. Bottled water or clean tap water will be used for the rectal douches. Bottled water will be provided by the sites for participants who are unable to obtain clean tap water. Supplies and instructions for preparing the rectal douches will be provided to the study participants.

#### ***Placebo Rectal Suppository***

The MTN will oversee the manufacture of the placebo suppositories by CoreRx (Clearwater, FL).

### **6.4.2 Study Product Accountability**

The Clinical Research Site (CRS) Pharmacist of Record (PoR) is required to maintain complete records of the study products received and subsequently dispensed. All unused study products must be returned to the MTN LOC Pharmacist after the study is complete unless otherwise instructed by the MTN LOC Pharmacist.

## **6.5 Study Product Dispensing**

Study products will be dispensed by the pharmacist to study staff upon receipt of a written prescription from an authorized prescriber. An authorized prescriber includes the IoR or a licensed clinician directly responsible to the IoR as noted on the DAIDS IoR Form. Study product will be dispensed at the beginning of each product use period including Enrollment (Day 0), Visit 4 (Day 35), and Visit 6 (Day 70). If additional supplies are needed between study visits, participants will be instructed to contact the study site.

## 6.6 Ancillary Study Supplies

Participants will be offered male condoms at all visits. The condoms will be made available in the clinic and will be dispensed by the clinic staff. Participants will be provided lubricant approved for use during the product administration periods to facilitate insertion. At all other visits, clinical staff will offer participants lubricant (not containing N-9) as per local standard of care.

## 6.7 Concomitant Medications and Practices

Enrolled study participants may use concomitant medications during study participation. All concomitant medications reported throughout the course of the study will be recorded in the study database. Concomitant medications include all prescription medications, over-the-counter preparations, vitamins, nutritional supplements, and herbal preparations.

[figure not shown]
Use of rectally-administered non-study medications and products is prohibited, including any products containing N-9.

*Note: The use of non-study personal lubricants and usual pre-RAI douches that do not contain N-9 is permitted during study participation*

# 7 STUDY PROCEDURES

An overview of the study visit and evaluations schedule is presented in [Appendix I](#). Presented in this section is additional information on visit-specific study procedures. Detailed instructions to guide and standardize procedures as well as information regarding the study visit windows are provided in the MTN-035 SSP Manual available at <http://www.mtnstopshiv.org/research/studies>.

Figure 2: MTN-035 Study Visit Schedule

## 7.1 Pre-screening

As part of participant outreach and recruitment strategies, study staff can pre-screen potential study participants at either on-site or off-site locations. During these interactions, study staff may explain the study to potential participants and ascertain elements of presumptive eligibility (e.g., willingness to use the study products, willingness to adhere to the study requirements, etc.), to be confirmed at an on-site screening visit. Process information (e.g., number of potential participants contacted, number presumptively eligible) may be recorded and stored at the study site in the absence of written informed consent from potential participants, provided the information is collected in such a manner that it cannot be linked to participant identifiers, unless a waiver is granted from the local IRB/IEC. Procedures and documentation will comply with local IRB/IEC requirements.

